We plan to study the results for Sildenafil 20 - 40 mg orally two times a day (a dosage used in treating pulmonary hypertension) in treating vitelliform degeneration or dry AMD, including patients who have had wet AMD in the fellow eye. A small cohort of patients who have a form of dry AMD termed Reticular AMD will also be studied. This form of AMD has small drusen that present as "pox-like" finely scattered drusen that can progress to AMD. Patients with Reticular AMD offer the advantage of small lipid volume and thus are a potentially easier group to quantify resolution using a PDE-5 and PDE-6 inhibitor such as Sildenafil. In addition, we will include other degenerative diseases of the choroid and retina as well as hereditary and acquired retinal

dystrophies, such as central serous retinopathy and retinitis pigmentosa, that may benefit from increased choroidal blood flow.

Study Design

Patients will be enrolled to receive Sildenafil as part of the study. We will also review records of patients who are receiving Sildenafil as part of their standard of care. The study will enroll up to 25 patients with dry AMD, reticular AMD or a combination of wet and dry AMD as well as other macular, retinal and choroidal degenerations and dystrophies. The visual acuity and ocular coherent tomography (OCT) evaluation will be performed as noted under study procedures. We plan to continue the study until up to 25 patients have completed five years of follow-up. This will include patients who are receiving Sildenafil as part of the study and patients who receive Sildenafil for standard care whose charts will be reviewed.

Criteria of visual acuity and number of Lucentis (or other anti-VEGF drugs) injections will be monitored and compared with well documented studies using Lucentis or Avastin or Eylea. OCT and ultrasound measurement of drusen change will be performed and quantified by size and number of drusen.

Patients referred for diagnosis and treatment of AMD as well as other macular, retinal and choroidal degenerations and dystrophies in the practices of Columbia Ophthalmology doctors will be offered inclusion in the study if they have drusen and normal vision in at least one eye. In the course of the study, measurements of vision and Optical Coherence Tomography (OCT). Fundus photography will also be performed at initial exam and if changes are noted on OCT or clinical exam. Visual acuity will be measured.

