Systemic Sildenafil will be prescribed for twice a day use. Initial Sildenafil dosage will be weight dependent. Patients will start at 40 mg daily (20 mg in the morning, 20 mg in the evening) or 60 mg daily (40 mg in the morning and 20 mg in the evening). The patient will be followed monthly or bi-monthly as is usual. Sildenafil dosage may be increased to up to 80mg daily (20-40mg in the morning and 20-40mg in the evening) based on the response to lower doses. If the subject has not had improvement after initial treatment, their dose may be increased, at the discretion of the study physician.

Visual acuity along with OCT will be performed at each visit. If available, ultrasound perfusion measurements will be performed within approximately 6 months of starting medication

and approximately 12 months after starting medication. Patients will be treated with Sildenafil only if they choose to enroll in the study.

Patients with AMD will continue to take sildenafil until otherwise directed. Patients with retinal dystrophies and degenerations will take sildenafil until otherwise directed. Patients with central serous retinopathy and other dystrophies with fluid-filled structures will stop one month after OCT testing shows a resorption of fluid from ocular structures. If the fluid-filled structures return, we may restart sildenafil treatment after observing these structures on OCT.

STATISTICAL PROCEDURES

Statistical evaluation will be provided for data using a standard T-test. Patients will be asked to participate for a period of up to 5 years. Results are deterministic, either drusen will improve or they will not. Secondly, the period between injections for wet AMD will be extended or not, compared to the standard treatment protocol. Improvement or maintenance from baseline of visual acuity, contrast sensitivity and OCT and fundus appearance are the end points.

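### The only named method is a t-test, while the drusen and injection results are stated as yes/no and called deterministic, so those results have either an ill-fitting test or no statement of uncertainty

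*Combined protocol and SAP*

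**What the plan says.** The Statistical Procedures section of the combined protocol and SAP gives one method for everything: "Statistical evaluation will be provided for data using a standard T-test". It does not say whether the test is one-sample, paired or two-sample, or which variables it covers.

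After a sentence on length of participation, the section states two results in yes/no form. The first is "Results are deterministic, either drusen will improve or they will not". The second is "Secondly, the period between injections for wet AMD will be extended or not, compared to the standard treatment protocol". The endpoints follow: "Improvement or maintenance from baseline of visual acuity, contrast sensitivity and OCT and fundus appearance are the end points". This wording also reads as a classification into success or failure, although some of the underlying measures are numeric.

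The Study Design section does plan numeric data: "OCT and ultrasound measurement of drusen change will be performed and quantified by size and number of drusen". Visual acuity and the number of anti-VEGF injections are also to be followed. On size, "The study will enroll up to 25 patients with dry AMD, reticular AMD or a combination of wet and dry AMD", together with other degenerations and dystrophies, so 25 is the ceiling for the whole mixed group.

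The documents give no confidence level, alpha, expected response rate, reference rate or method for a proportion.

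**The concern.** A yes/no outcome is not deterministic in the statistical sense. The share of patients who improve, out of at most 25, is an estimate with sampling error, and a report that leaves the error out conveys more certainty than the data hold.

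The one method on offer does not repair this. A t-interval on 0/1 data takes its standard deviation from the observed proportion. As that proportion nears 0 or 1, the standard deviation shrinks and the symmetric interval can run past the possible range. When every patient has the same result, the standard deviation is zero and the interval collapses.

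Two features of the plan make such cases plausible, though not certain. Counting maintenance as success can push a proportion high. The injection-interval result concerns wet AMD only, so its denominator is probably below 25. At stake is whether a clean-looking result, such as every patient maintained, is reported with its real uncertainty.

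**Working it through.** The plan has no figure of its own to reproduce: the limit of 25 has no derivation, and no power or precision is stated.

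**Inputs.** From the documents: n of at most 25, yes/no outcomes, and a t-test as the only method. Assumed: two-sided 95% intervals, response rates from 0.5 to 0.98 (low rates mirror high ones), and n = 10 as an example subgroup.

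**Formulas.** For x successes in n, p = x/n and s² = n·p·(1 − p)/(n − 1). The t-interval is p ± t(0.975, n − 1)·s/√n. With n = 25, t(0.975, 24) = 2.064. Coverage is the sum of binomial probabilities over all x whose interval contains the true rate; a zero-width interval counts as not covering. The exact comparison is Clopper-Pearson.

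**Limits outside the possible range, n = 25.** For 23/25, p = 0.92, s = 0.277 and the half-width is 2.064 × 0.277/5 = 0.114.

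| Result | t-interval | Exact interval |
|---|---|---|
| 20/25 | 63.1% to 96.9% | 59.3% to 93.2% |
| 22/25 | 74.3% to 101.7% | 68.8% to 97.5% |
| 23/25 | 80.6% to 103.4% | 74.0% to 99.0% |
| 24/25 | 87.7% to 104.3% | 79.7% to 99.9% |
| 25/25 | 100% to 100% | 86.3% to 100% |

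Only 22, 23 and 24 of 25 exceed 100%; 1, 2 and 3 of 25 fall below 0%. At 25/25 the exact lower limit is 0.025^(1/25) = 0.863. The t statistic there is infinite, or undefined (0/0) if the reference value is itself 100%.

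**Coverage of the nominal 95% t-interval.**

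| n | True rate | t coverage | Chance all agree |
|---|---|---|---|
| 25 | 0.5 | 95.7% | below 0.1% |
| 25 | 0.7 | 94.9% | below 0.1% |
| 25 | 0.8 | 89.6% | 0.4% |
| 25 | 0.9 | 92.6% | 7.2% |
| 25 | 0.95 | 72.1% | 27.7% |
| 10 | 0.8 | 88.6% | 10.7% |
| 10 | 0.9 | 65.0% | 34.9% |

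On a fine grid of rates from 0.3 to 0.7 at n = 25, coverage runs from 92.3% to 96.7%, with a mean of 94.6%.

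**Where the loss comes from.** At n = 25 and rate 0.95, the chance that all agree is 0.95^25 = 0.277 (the chance that all fail is negligible). Given that an interval of positive width exists, coverage is 0.7214/(1 − 0.2774) = 0.998. At n = 10 and rate 0.9 it is 0.6497/(1 − 0.3487) = 0.9975. So at those rates the low coverage and the all-agree case are almost the same event and should not be counted twice. At n = 25 and rate 0.8 the shortfall is separate: coverage is 0.8962/(1 − 0.0038) = 0.900 even when an interval exists.

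**The alternatives.** At n = 25 and the rates checked from 0.5 to 0.98, Clopper-Pearson coverage is at least 95.7% (97.9% at 0.8, 99.3% at 0.95). Wilson coverage lies between 91.1% and 96.7%.

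**The case against.** The strongest reply is that the plan never ties the t-test to the yes/no results. The t-test sentence speaks of data in general, and a sentence on participation length stands between it and the claim of determinism. The Study Design section plans numeric measures for which a t-test is reasonable, and time between injections is itself a duration. The yes/no sentences may only describe what the study will conclude. This stands in part: a reader might infer that the plan commits to t-tests on 0/1 outcomes, and the text does not say that. But on the narrower reading the yes/no results have no method at all, and the word deterministic excuses them from one. The same correction is needed either way.

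A reader might also infer that the t-test generally gives impossible limits and far too low coverage. The arithmetic does not support this. At 25 patients and middle rates it performs acceptably, and the 72% and 65% coverages are the zero-variance case seen from another side.

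Nor can it be said that the plan's reported limits will be wrong, because it promises none. An error rate against a reference can be computed: with an assumed reference of 80%, a two-sided 5% t-test rejects upward at 23 or 24 of 25, with probability 0.071 + 0.024 = 9.4% (rounded from 0.0944) against a nominal 2.5%. But the plan states no reference, so this is an illustration and not a property of the plan.

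Finally, defining improved and extended matters more than the choice between two interval methods. That is fair as an order of priorities. It does not remove the need for a method.

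**Conclusion.** The concern holds in conditional form. The statistics section leaves its yes/no results with either a method that fits them poorly or no expression of uncertainty, and describing them as deterministic is wrong.

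The practical size depends on rates that the documents do not give. If the true rates are moderate and all 25 patients contribute, a t-interval would do little harm. If rates are very high or very low, or a result rests on about 10 patients, it can show limits beyond 0% or 100%, or no uncertainty at all. The clearest example is unanimity: 25 of 25 would appear as certainty although rates down to 86.3% remain compatible with the data, and for 10 of 10 the exact lower limit is 0.025^(1/10) = 69.2%. All figures assume two-sided 95% intervals and independent patients. This should be corrected, but the correction is small.

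**What to change.** In Statistical Procedures:

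- Restrict the t-test to changes in numeric measures, such as drusen size and number, visual acuity and number of injections.
- Report any result kept as yes/no as a count and a proportion, with its denominator and an exact (Clopper-Pearson) or Wilson 95% interval.
- Add an exact binomial test only where a reference rate is stated in advance.
- Delete the statement that results are deterministic.

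This takes one or two sentences and changes nothing in data collection. The price is that exact intervals are somewhat conservative and therefore wider, with coverage of about 98% to 99% at rates of 0.8 to 0.95 with 25 patients. Wilson intervals avoid most of that, but their coverage can dip below 95%.
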